6.0 DOSE MODIFICATIONS

Toxicities should be attributed to a specific study drug if possible so that dose modifications can be made rationally. If multiple toxicities are noted, the dose adjustments and or/delays should be made once per cycle according to the guidelines for the most severe toxicity. The maximum delay before treatment should be discontinued will be 3 weeks unless permission to resume treatment is granted by the Principal Investigator. Alternative dose modifications than those listed below may be recommended in order to maximize exposure of study treatment while protecting patient safety.

6.1 Dose Levels

Ixazomib Dose Levels

Dose Level	Dose (mg)
Starting Dose	4.0 mg
-1	3.0 mg
-2	2.3 mg
-3	Discontinue

Lenalidomide Dose Levels for Consolidation Therapy

Dose Level	Dose (mg)
Starting Dose	15 mg
-1	10 mg
-2	5 mg
-3	Discontinue

Lenalidomide Dose Levels for Maintenance Therapy

Dose Level	Dose (mg)
+1	15 mg
Starting Dose	10 mg
-1	5 mg
-2	5 mg daily for 21 days every 8
-3	Discontinue

Dexamethasone Dose Levels

Dose Level	Dose (mg)
Starting Dose	40 mg
-1	20 mg
-2	8 mg
-3	Discontinue

6.2 Criteria for Beginning a New Treatment Cycle

For a new cycle of treatment to begin, the patient must meet the following criteria:

- ANC must be $\geq 1,000/\text{mm}^3$.
- Platelet count must be $\geq 75,000/\text{mm}^3$.
- All other treatment related non-hematologic toxicity (except for alopecia) must have resolved to \leq Grade 1 or to the patient's baseline condition

If the patient fails to meet the above-cited criteria for initiation of the next cycle of treatment, dosing should be delayed for 1 week. At the end of that time, the patient should be re-evaluated to determine whether the criteria have been met. If the criteria have been met, resume at previous dose levels.

If the patient continues to fail to meet the above-cited criteria, delay therapy and continue to re-evaluate weekly. If a delay of > 2 weeks is required, reduce the suspected drug(s) by one dose level when treatment is resumed. Dosing adjustments should not occur in both ixazomib and lenalidomide simultaneously.

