5.3.2 Ixazomib Administration

Ixazomib will be prescribed only to eligible patients under the supervision of the investigator or identified sub-investigator(s). Ixazomib will be administered on Days 1, 8, and 15 of a 28-day cycle at a starting dose of 4 mg. Sufficient quantity of drug for one cycle of therapy will be prescribed to the patient in Cycles 1-3 of maintenance therapy, and for three cycles of therapy in Cycles 4+.

Patients should be monitored for toxicity, as necessary, and doses of ixazomib should be modified as needed to accommodate patient tolerance to treatment; this may include symptomatic treatment, dose interruptions, and adjustments of ixazomib dose (see Section 6.0). Once ixazomib is reduced for toxicity, no dose re-escalation is permitted.

Ixazomib should be taken on an empty stomach (no food or drink), at least 1 hour before or 2 hours after a meal. Patients should be instructed to swallow ixazomib capsules whole and not to break, chew, or open the capsules. Each capsule should be swallowed separately with a sip of water. A total of approximately 8 ounces (240 mL) of water should be taken with the capsules.

Ixazomib should be taken at the same time each day. Missed doses can be taken as soon as the patient remembers if the next scheduled dose is 72 hours or more away. A double dose should not be taken to make up for a missed dose. Patients who vomit a dose after ingestion will not receive an additional dose, but should resume dosing at the time of the next scheduled dose.

If ixazomib maintenance is discontinued, crossover to the lenalidomide maintenance arm can occur if permission is granted by the Principal Investigator. Patients who crossover will continue to be followed per all protocol guidelines.

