5.3.3 Lenalidomide Administration

Lenalidomide will be prescribed only to eligible patients under the supervision of the investigator or identified sub-investigator(s). Lenalidomide will be administered daily continuously for a 28-day cycle at a starting dose of 10 mg. If lenalidomide is tolerated well (i.e. no dose modification required) during the first three cycles, lenalidomide dose will be increased to 15 mg daily. Sufficient quantity of drug for one cycle of therapy will be prescribed to the patient in Cycles 1-3, and for three cycles of therapy in Cycles 4+. Lenalidomide will be provided in accordance with the Celgene Corporation's Revlimid REMS® program.

VTE prophylaxis is not required during single-agent lenalidomide maintenance but is permissible at the discretion of the treating physician.

Patients should be monitored for toxicity, as necessary, and doses of lenalidomide should be modified as needed to accommodate patient tolerance to treatment; this may include symptomatic treatment, dose interruptions, and adjustments of lenalidomide dose (see Section 6.0).

If a lenalidomide dose reduction has occurred for hematologic toxicity and ANC $>1000/\mu\text{L}$ and platelet count is $>75,000/\mu\text{L}$, lenalidomide drug dose may be re-escalated one dose level per cycle to a maximum of 15 mg daily. If lenalidomide was reduced due to non-hematologic toxicity, no dose re-escalation is permitted.

Lenalidomide can be taken without regards to food or drink. Patients should be instructed to swallow lenalidomide capsules whole and not to break, chew, or open the capsules. Each capsule should be swallowed separately with a sip of water.

Lenalidomide should be taken at the same time each day. Missed doses can be taken as soon as the patient remembers if the next scheduled dose is 8 hours or more away. A double dose should not be taken to make up for a missed dose. Patients who vomit a dose after ingestion will not receive an additional dose, but should resume dosing at the time of the next scheduled dose.

If lenalidomide maintenance is discontinued, crossover to the ixazomib maintenance arm can occur if permission is granted by the Principal Investigator. Patients who crossover will continue to be followed per all protocol guidelines.

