6.3 Dosing Modifications for Hematologic Toxicities

6.3.1 Thrombocytopenia

Only thrombocytopenia determined to be related to one or more study drugs require dose reductions or adjustments as described in this section. Platelet transfusion support is permissible at the discretion of the treating physician. Participants who have treatment delayed for greater than 3 weeks should discontinue protocol therapy.

Dose modifications for thrombocytopenia during IRD Consolidation should be instituted as follows:

Grade	Platelet	Modification
3*	$< 50,000/\text{mm}^3$	First episode: Hold all drugs until platelets resolve to grade ≤ 1 , then reduce lenalidomide by one dose level Second episode: Hold all drugs until platelets resolve to grade ≤ 1 , then reduce ixazomib by one dose level Third episode: Hold all drugs until platelets resolve to grade ≤ 1 , then reduce lenalidomide by one dose level Fourth episode: Hold all drugs until platelets resolve to grade ≤ 1 , then reduce ixazomib by one dose level Fifth episode: Discontinue protocol therapy.

Dose modifications for thrombocytopenia during ixazomib or lenalidomide maintenance should be instituted as follows:

Grade	Platelet	Modification
3	< 50,000/mm ³	
First episode: Hold ixazomib/lenalidomide until platelets resolve to grade ≤ 1, then reduce ixazomib/lenalidomide by one dose level
 
Second episode: Hold ixazomib/lenalidomide until platelets resolve to grade ≤ 1, then reduce ixazomib/lenalidomide by one dose level
 
Third episode: Hold ixazomib/lenalidomide until platelets resolve to grade ≤ 1, then reduce ixazomib/lenalidomide by one dose level
 
Fourth episode: Discontinue protocol therapy.

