8.0 STUDY CALENDAR

Please note that all assessments allow a window of +/-3 days for scheduling issues.

	Screening		Consolidation ³			Restaging ⁴	Maintenance ⁵			EOS ⁷	F/U ⁸
	Prior to ASCT ¹	Prior to beginning consolidation ²	D1	D8	D15		D1	D8	D15		
Informed consent	X										
H&P, ECOG PS, plasmacytoma assessment	X	X	X ¹³			X	X ^{13,14}			X	X ¹⁵
CBC & CMP	X		X ¹³		X ⁶	X	X ^{13,14}			X	
SPEP and immunofixation	X	X	X ¹³			X	X ^{13,14}			X	
24h urine for total protein, UPEP, and immunofixation ⁹	X	X	X ¹³			X	X ^{13,14}			X	
Serum-free light chains & β2 microglobulin	X	X	X ¹³			X	X ^{13,14}			X	
Quantitative immunoglobulins (IgA, IgG, IgM)	X	X	X ¹³			X	X ^{13,14}			X	
Serum βhCG ¹⁰	X	X	X				X			X	
Bone marrow biopsy and aspirate ¹¹	X	X				X	X ¹⁶				
Central labs ¹² (MRD Analysis)		X				X	X ¹⁶				
Central labs ¹² (Hevylite)	X		X ¹³			X	X ^{13,14}			X	
Central labs ¹⁸ (Sub-study)		X ¹⁸					X ¹⁸				
Ixazomib			X	X	X		X	X	X		
Lenalidomide			Days 1-21				Days 1-28				
Dexamethasone			X	X	X						
Administration Questionnaire ¹⁷			X				X				
Adverse events assessment			X ----- X								

1. Day -60 to Day -2

2. Day +80 to Day +120; to occur within 28 days prior to C1D1 of consolidation

3. 4 28-day cycles

4. Prior to beginning maintenance (approx. Day +192 to Day +232); to occur within 28 days after completing C4 of consolidation and within 28 days prior to C1D1 of maintenance

5. 28-day cycles; continued until progression or unacceptable toxicity

6. Cycles 1-2 only

7. Within 30 days of last dose of study drug(s)

8. Every 3 months for 18 months

9. Repeat 24h urine only required for patients with ≥ 200 mg/24h of M-protein at screening

10. Women of childbearing potential only; 2 negative tests are required within 14 days before study drug dosing on C1D1 of consolidation

11. Bone marrow aspirate and core biopsy – differential required; Cytogenetics, and fluorescent *in situ* hybridization (FISH) studies performed per institutional guidelines.

12. See Section 9.0

13. Not required on C1D1 if screening/restaging visit occurred within 28 days prior

14. C1-C4 then every 3 cycles thereafter (i.e., C7, C10, C13 ...)

15. A telephone call to assess OS and PFS can be made in lieu of a physical exam

16. Cycle 13 for all patients. Cycle 25 and 37 also required for patients in suspected or confirmed CR/sCR at that time.

17. See Appendix D. Patient to complete following each cycle of study treatment (consolidation and maintenance).

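### From maintenance cycle 5, the blood counts that Section 6.2 requires before each new cycle are scheduled at only one cycle start in three

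*Combined protocol and SAP*

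**What the plan says.** Section 6.2 sets the conditions for starting a cycle: "For a new cycle of treatment to begin, the patient must meet the following criteria". They are ANC at or above 1,000/mm3, platelets at or above 75,000/mm3, and recovery of treatment-related non-hematologic toxicity to Grade 1 or baseline.

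Nothing in Section 6.2 confines the rule to consolidation. Section 6.0 covers both phases: Section 6.1 has a separate table of maintenance lenalidomide dose levels, and Section 6.3 names the phase where a rule is specific to one, as in "Dose modifications for thrombocytopenia during ixazomib or lenalidomide maintenance should be instituted as follows".

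In the Section 8.0 calendar, CBC and CMP share one row. In maintenance that row is marked on Day 1 only, subject to notes 13 and 14. Note 13 concerns C1D1 alone. Note 14 sets the frequency: "C1-C4 then every 3 cycles thereafter (i.e., C7, C10, C13" and so on. The calendar also states that "all assessments allow a window of +/-3 days for scheduling issues".

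Prescribing follows the same rhythm. For ixazomib (Section 5.3.2), enough drug for one cycle "will be prescribed to the patient in Cycles 1-3 of maintenance therapy, and for three cycles of therapy in Cycles 4" and beyond. Section 5.3.3 says the same for lenalidomide, and raises the dose from 10 to 15 mg after three cycles that needed no dose modification.

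**The concern.** From C5, two of every three maintenance cycles begin under a mandatory count criterion with no count scheduled to test it. The third criterion in Section 6.2 is not at issue, because adverse events are assessed throughout treatment.

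The consequences are practical:

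- The wide spacing begins when lenalidomide rises to 15 mg in patients who tolerated C1-C3.
- Section 5.3.3 allows lenalidomide to be re-escalated one level per cycle if ANC and platelets are adequate. From C5 that decision also needs counts the calendar does not supply.
- Section 6.3 holds and reduces drug at platelets below 50,000/mm3 or ANC below 1,000/mm3. An episode falling between scheduled counts may be found late or missed.
- Sites can reasonably differ: one may draw an off-calendar count before every cycle, another may follow the calendar.

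**Working it through.** No power or alpha calculation is involved. The check counts cycle starts against the calendar.

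**Inputs.** Section 6.2: count criteria apply to each new cycle. Section 8.0: CBC on maintenance Day 1, note 14 frequency, 28-day cycles, window of 3 days either side. Note 16: C37 is the last marrow time point, used here as an illustrative end because maintenance is open-ended.

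**1. The plan's own schedule.** Starting from C4 and adding 3 each time gives C7, C10, C13, which is the note 14 list. C1-C4 are all listed, so C5 is the first maintenance start without a scheduled count.

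**2. Coverage, C5-C37.**
- Cycle starts: 37 - 5 + 1 = 33.
- With a scheduled CBC: C7, C10, C13, C16, C19, C22, C25, C28, C31, C34, C37 = 11.
- Without: 33 - 11 = 22, and 22/33 = 66.7%.

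**3. Spacing from C4.**
- C4D1 to C7D1: 3 x 28 = 84 days.
- With 3 days' tolerance at each end: 84 - 6 = 78 to 84 + 6 = 90 days.
- The same interval separates the C4 lenalidomide increase from the next scheduled count.

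**4. Whether other text fills the gap.**
- Sections 6.5.5 and 6.5.6 refer back to monitoring under the protocol and add testing under standard practice. They give no frequency.
- Section 10.0 lists a Safety Labs Form for each cycle. The same row lists an MM Labs Form for each cycle, although the myeloma tests also carry note 14. The form list therefore does not show that a test is ordered every cycle.

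**5. Extra counts needed to cover every start.**
- Per patient-year: (365.25/28) x 2/3 = 8.70.
- Check: 33 x 28 = 924 days = 2.53 years, and 22/2.53 = 8.70.
- Ceiling, assuming all of about 240 patients (Section 15.0) are on maintenance beyond C4 at once: 8.70 x 240 = 2,088, or about 2,090 a year.

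**6. After the change.** Coverage over C5-C37 becomes 33 of 33, and nominal spacing falls from 84 to 28 days.

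**The case against.** The strongest reply is that the calendar is not the only source of required counts. Section 6.2 is mandatory and cannot be satisfied without a count. Sections 6.2 and 6.3 already call for re-evaluation and recovery checks that have no calendar slot, and the per-cycle Safety Labs Form suggests that labs every cycle may have been expected. On this reading the defect is a missing cross-reference. This stands in part: a site that obeys Section 6.2 will draw the count. But the calendar sets an explicit, lower frequency for that very test and does not point to Section 6.2, so the two instructions still conflict.

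A second reply is that three-cycle prescribing from C4 matches note 14, so quarterly monitoring may be deliberate. The last sentence of Section 6.2, about not adjusting both drugs together, also fits consolidation better. The documents give no late-maintenance cytopenia rate to show that 84 days is unsafe. That is fair. But if quarterly counts are intended, Section 6.2 is wrong as written from C5 and still needs changing.

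A reader might go further in three ways that the documents do not support:

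- **That patients will be dosed through unrecognised cytopenias, or hold three cycles of drug unsupervised.** Extra counts are allowed, and the documents do not say how much drug a patient holds at once.
- **That the toxicity comparison between maintenance arms is biased.** Both arms follow the same CBC row. Detection may vary with site practice, but nothing shows a difference by arm.
- **That consolidation is a fully covered contrast.** The CBC row as extracted shows no mark at the pre-consolidation visit, and note 13 waives C1D1 when that visit fell within 28 days, as note 2 requires. No such contrast is drawn here.

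**Conclusion.** The inconsistency is real and should be corrected. From C5, the calendar supports the Section 6.2 count criteria at one maintenance cycle start in three. The count is exact given note 14 and undelayed 28-day cycles; C37 is only a convenient stopping point. What follows clinically is less certain: late detection depends on a site drawing calendar tests only. This is a matter of safety and conduct. The primary endpoint is measured over consolidation, so it is unaffected, as are sample size, power and alpha.

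**What to change.** Remove the note 14 limit from the CBC alone, and require a local-laboratory CBC with differential before Day 1 of each maintenance cycle. CMP, myeloma labs and clinic visits stay on note 14. State in Sections 5.3.2 and 5.3.3 that the next cycle starts only after the site confirms the Section 6.2 criteria. Record the result on the existing per-cycle Safety Labs Form, so no new form is needed.

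The cost is one protocol amendment, with local IRB submission by the secondary sites under Section 16.0, and 2 further routine counts per 84 days. That is 22 per patient over C5-C37, within the yearly ceiling worked out above. Some patients may need extra trips to a local laboratory. Women of childbearing potential could combine the count with the Day 1 serum hCG draw, which as extracted carries no note 14 limit in maintenance.

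If the sponsor intends quarterly counts, the smaller change is to limit the Section 6.2 count criteria expressly to cycles with a scheduled visit. That removes the conflict but leaves the 84-day monitoring gap, and the choice should then be justified.

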6.3 Dosing Modifications for Hematologic Toxicities

6.3.1 Thrombocytopenia

Only thrombocytopenia determined to be related to one or more study drugs require dose reductions or adjustments as described in this section. Platelet transfusion support is permissible at the discretion of the treating physician. Participants who have treatment delayed for greater than 3 weeks should discontinue protocol therapy.

Dose modifications for thrombocytopenia during IRD Consolidation should be instituted as follows:

Grade	Platelet	Modification
3*	$< 50,000/\text{mm}^3$	First episode: Hold all drugs until platelets resolve to grade ≤ 1 , then reduce lenalidomide by one dose level Second episode: Hold all drugs until platelets resolve to grade ≤ 1 , then reduce ixazomib by one dose level Third episode: Hold all drugs until platelets resolve to grade ≤ 1 , then reduce lenalidomide by one dose level Fourth episode: Hold all drugs until platelets resolve to grade ≤ 1 , then reduce ixazomib by one dose level Fifth episode: Discontinue protocol therapy.

Dose modifications for thrombocytopenia during ixazomib or lenalidomide maintenance should be instituted as follows:

Grade	Platelet	Modification
3	< 50,000/mm ³	
First episode: Hold ixazomib/lenalidomide until platelets resolve to grade ≤ 1, then reduce ixazomib/lenalidomide by one dose level
 
Second episode: Hold ixazomib/lenalidomide until platelets resolve to grade ≤ 1, then reduce ixazomib/lenalidomide by one dose level
 
Third episode: Hold ixazomib/lenalidomide until platelets resolve to grade ≤ 1, then reduce ixazomib/lenalidomide by one dose level
 
Fourth episode: Discontinue protocol therapy.

Dyspepsia, Gastric or duodenal ulcer, or Gastritis	2	Each episode: Treat with histamine-2 blockers, sucralfate, or omeprazole as needed. If symptoms persist despite these measures, decrease dexamethasone by 1 dose level.
Pancreatitis	2	First episode: Discontinue dexamethasone.
Peripheral Neuropathy with pain	2	Each episode: Hold suspected study drug(s) until toxicity resolves to \leq grade 1 or baseline, then reduce suspected drug(s) by one dose level.
Muscle Weakness	2	
First episode: Decrease dexamethasone by one dose level.
 
Second episode: If weakness persists, decrease dexamethasone by one more dose level.
 
Third episode: Discontinue dexamethasone

Toxicity	Grade	Modification
Rash	2	Each episode: Hold suspected study drug(s) until toxicity resolves to \leq grade 1 or baseline, then restart at previous dose level once at the investigator's discretion.
Thrombosis or Embolism	2	Each episode: Hold lenalidomide and commence anticoagulation therapy, then restart at previous dose level at the investigator's discretion.
Diarrhea	3	Each episode: Only if the event occurred despite optimal supportive therapy, Hold suspected study drug(s) until toxicity resolves to \leq grade 1 or baseline, then reduce suspected drug(s) by one dose level.
Dyspepsia, Gastric or duodenal ulcer, or Gastritis	3	First episode: Hold dexamethasone until toxicity resolve to \leq grade 1 or baseline, then decrease dexamethasone by 1 dose level. Prophylactically treat with histamine-2 blockers, sucralfate, or omeprazole as needed. Second episode: If symptoms persist despite these measures, discontinue dexamethasone.
Edema	3	First episode: Treat with diuretics as needed. Decrease dexamethasone by one dose level. Second episode: If edema persists, decrease dexamethasone by one more dose level. Third episode: Discontinue dexamethasone
Fatigue	3	Each episode: No modification required.
Hyperglycemia	3	Each episode: Treat with insulin or hypoglycemic as needed. If uncontrolled despite these measures, decrease dexamethasone by 1 dose level.
Nausea/Vomiting	3	Each episode: Only if the event occurred despite optimal anti-emetic prophylaxis, Hold suspected study drug(s) until toxicity resolves to \leq grade 1 or baseline, then reduce suspected drug(s) by one dose level.
Rash Exfoliative or bullous rash; Stevens-Johnson Syndrome, toxic epidermal necrolysis or Angioedema suspected	3	First episode: Discontinue suspected study drug(s).
Other non-hematologic toxicity	3	Each episode: Hold suspected study drug(s) until toxicity resolves to \leq grade 1 or baseline, then reduce suspected drug(s) by one dose level.

Toxicity	Grade	Modification
Other non-hematologic toxicity	4	Each episode: Discontinue protocol therapy unless principal investigator grants permission to continue

6.5 Management of Clinical Events

Adverse drug reactions such as thrombocytopenia, diarrhea, fatigue, nausea, vomiting, and rash have been associated with ixazomib treatment. Management guidelines regarding these events are outlined below. Further details of management of ixazomib AEs are described in Section 6 of the ixazomib IB.

6.5.1 Prophylaxis against Risk of Reactivation of Herpes Infection

Patients may be at an increased risk of infection including reactivation of herpes zoster and herpes simplex viruses. Antiviral therapy such as acyclovir, valacyclovir, or other antivirals may be initiated as clinically indicated. Other antivirals are also acceptable.

6.5.2 Nausea and/or Vomiting

Standard anti-emetics including 5-hydroxytryptamine 3 serotonin receptor antagonists are recommended for emesis if it occurs once treatment is initiated; prophylactic anti-emetics may also be considered at the physician's discretion. Dexamethasone should not be administered as an anti-emetic. Fluid deficit should be corrected before initiation of study drug and during treatment.

6.5.3 Diarrhea

Prophylactic antidiarrheals will not be used in this protocol. However, diarrhea should be managed according to clinical practice, including the administration of antidiarrheals once infectious causes are excluded. Fluid intake should be maintained to avoid dehydration. Fluid deficit should be corrected before initiation of treatment and during treatment.

